#### 4.2 Adverse Effects

In this study, adverse effects are defined as undesired effect that occurs medication is administered. We will use Scripted Prompting, a proactive form of adverse effect capture recognized in the field. This method is designed to elicit adverse effects without biasing the patient; it is a standardized question that allows participant to report important symptoms without being influenced by suggestion. For this study we will ask: *“Since initiating medical marijuana are you having any problems related to use?”*

To describe factors associated with adverse effects we will report the number of adverse effects reported by participants at time points 2 and 3. Adverse Effects will be defined as both a count variable and a binary variable such that absence or presence of adverse effects will be coded as 0/1 respectively. We will then use Poisson and Logistic regression methods to examine analyze the bivariate association between dosage, frequency of use, route of administration (pills, vape, etc.), and type of product (THC v. CBD). Limitations may be related to the frequency and distribution of events leading to complete or quasi-separation of data points. Possible mitigations would be re-categorization of explanatory variables, exact or firth regression, or a different functional form of the model.

PROTOCOL TITLE: Medical Marijuana Use and Driving Performance: A Test of Psychomotor Function in Adults 50 and Older.

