We will recruit N=60 participants total. Participants will be eligible for the current study if they: a) report severe or chronic pain; b) are age 50 or older; c) are newly registered for the Medical Marijuana Registry in the State of Florida; d) have no prior history of medical marijuana use; e) can communicate in English; and f) are willing and able to complete study procedures or if they meet control group criteria: (n=30) Medical Marijuana Users **or** (n=30) Age, Gender, Race Matched Controls. Persons will be ineligible if they: a) meet

**PROTOCOL TITLE:** Medical Marijuana Use and Driving Performance: A Test of Psychomotor Function in Adults 50 and Older.

criteria for current or past alcohol and/or illicit drug dependence; b) have vertigo or any vestibular systems dysfunction (due to the to develop simulator adaptation syndrome); c) screen high on the simulator sickness prescreen; d) use contraindicated medication (benzodiazepines, beta blockers, antihistamines, or sedatives) from which they cannot abstain due to medical reasons; and/or e) are planning to move out of the area within 6 months.

We will recruit patients in the control group within the local community. This will happen by placing recruitment flyers in public places (i.e. grocery stores, libraries, senior living communities, etc.). Additionally, we will utilize Consent2Share, an initiative of the UF Integrated Data Repository (IDR) and supported by UF CTSI (Clinical and Translational Science Institute) that allows for a large group of potential research participants who have consented to be re-contacted for future research studies. The control group will be matched by age, gender and race. Control subjects will be ineligible if they: a) meet criteria for current or past alcohol and/or illicit drug dependence; b) have vertigo or any vestibular systems dysfunction (due to the to develop simulator adaptation syndrome); c) screen high on the simulator sickness prescreen; d) use contraindicated medication (benzodiazepines, beta blockers, antihistamines, or sedatives) from which they cannot abstain due to medical reasons; and/or e) are planning to move out of the area within 6 months, f.) have a history of marijuana use. Control subjects will be used to ensure results are not attributed to a simple change in time. Results will provide evidence for the effects of medical marijuana use on the real work task among adults 50 and older.

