6.8 Adverse Effects: In this study, adverse effects are defined as undesired effect that occurs when the medical marijuana is administered. We will use Scripted Prompting, a proactive form of adverse effect capture recognized in the field. This method is designed to elicit adverse effects without biasing the patient; it is a standardized question that allows participant to report important symptoms without being influenced by suggestion. For this study we will ask: "*Since initiating medical marijuana, are you having any problems related to use?*"

6.9 Control Procedures: Control participants will be community-dwelling age, race, and gender matched.

6.10 Participant Retention: We will develop a strong collaborative relationship between participants and members of the research team through empathy, encouragement and skill building.

6.11 Three- and Six-Month Follow-Up Assessment: The second assessment (T2) will occur one month after the participant has been dispensed medical marijuana for the first time. T3 will occur 3 months after the participant has been dispensed medical marijuana for the first time. The follow-up assessments will consist of a minimally reduced psychosocial assessment battery, and the same simulator adaptation and main drive (described above). All participants will be paid \$50 per assessment visit (\$150 total across all visits over the 3 month period). Participants

**PROTOCOL TITLE:** Medical Marijuana Use and Driving Performance: A Test of Psychomotor Function in Adults 50 and Older.

will not be paid for screening assessments or chart abstracted data. Data will be collected using both self-directed methods such as ACASI with headphones or self-administered on paper and Research Assistant administered tasks. The Baseline Assessment is expected to take approximately 90 minutes, and follow-ups will take approximately 60 minutes. Though it is time-consuming, we do not anticipate participant barrier as a burden based on prior work.

[figure not shown]

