## **17.0 Data Management\* and Confidentiality**

17.1 **Test of Aim 1 (Driving Simulator):** Between group (medical marijuana users vs controls) comparisons will first be examined using independent samples t-test (controlling for unequal variances using Levene's test) or Mann-Whitney U tests if the data are nonparametric. Repeated measures ANOVA will be used to examine within participants differences on measures at all 3 time points in order to answer the question of whether medical marijuana impacts response time, divided attention, and executive functions.

Limitations may be related to the distribution of the dependent and independent variables. Possible mitigation approaches include creating a dichotomous variable of high versus low for outcomes and using logistic regression or other functional form as dictated by the distribution of the dependent and independent variables.

17.2 **Test of Aim 2 (Adverse Effects):** To describe factors associated with adverse effects we will report the number of adverse effects reported by participants at time points 2 and 3. Adverse Effects will be defined as both a count variable and a binary variable such that absence or presence of adverse effects will be coded as 0/1 respectively. We will then use Poisson and Logistic regression methods to examine analyze the bivariate association between dosage, frequency of use, route of administration (pills, vape, etc.), and type of product (THC v. CBD). Limitations may be related to the frequency and distribution of events leading to complete or quasi-separation of data points. Possible mitigations would be re-categorization of explanatory variables, exact or firth regression, or a different functional form of the model. The goal of aim 2 is to examine the strength of the association between factors of medical marijuana use and adverse effects. As there may be insufficient power for statistical

PROTOCOL TITLE: Medical Marijuana Use and Driving Performance: A Test of Psychomotor Function in Adults 50 and Older.

significance, effect size estimates (Cohen's d) will be used to examine the strength of the association between variables.

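### The Aim 2 adverse-effect count is analysed by plain Poisson regression with nothing specific on dispersion, so its standard errors are right only if the variance equals the mean

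*Combined protocol and SAP*

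**What the plan says.** Section 4.2 sets up the outcome in two ways: "Adverse Effects will be defined as both a count variable and a binary variable". Section 17.2 adds that "we will report the number of adverse effects reported by participants at time points 2 and 3", and then: "We will then use Poisson and Logistic regression methods to examine analyze the bivariate association between dosage, frequency of use", with route of administration and product type completing the list. Each factor is therefore taken one at a time.

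The data come from one open prompt: "Since initiating medical marijuana are you having any problems related to use". Section 6.1 plans 30 users. Controls have no dose, product or route, so Aim 2 rests on those 30.

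The foreseen difficulty is this: "Limitations may be related to the frequency and distribution of events leading to complete or quasi-separation of data points". The remedies offered are recategorising the explanatory variables, exact or Firth regression, or an unspecified change of model form. Neither 4.2 nor 17.2 mentions a dispersion check, a scaled or negative binomial model, or robust standard errors. Neither says how the T2 and T3 reports are combined into a count.

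Section 17.2 gives the aim as strength of association, concedes that power may be too low for significance, and turns to effect sizes.

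**The concern.** Poisson regression takes the variance from the mean instead of estimating it. If some users report several problems and many report none, the true variance exceeds the mean and the printed standard errors are too small. If nearly everyone reports none or one, the variance falls below the mean and they are too large. Either way the intervals for dose, frequency, product and route are miscalibrated, and the fitting routine gives no warning.

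The prompt refers back to initiation and is put at both T2 and T3. If the two visits are summed, a persisting problem counts twice, which by itself raises variance/mean. Fitting one factor at a time also leaves variation due to the other factors in the residual.

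What is at stake is a false signal, or a falsely precise one, about THC products, vaporizing or higher dose. Section 1.1.3 names best-practice guidelines as the long-range goal.

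**Working it through.** **Plan's own figure.** There is none for Aim 2. The only power calculation, in 17.4, concerns Aim 1 and has no bearing here.

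**Inputs.** From the documents: 30 users (6.1), Poisson regression with one factor at a time (17.2). Assumed, because the documents are silent: two-sided 5% level, a mean of 1 problem per user (0.5 and 2 also tried), and variance/mean φ of 1.5, 2 and 3, with 0.6 for the opposite direction.

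**Step 1: standard error.** If the variance is φ times the mean, the true standard error is √φ times the Poisson one: √1.5 = 1.22, √2 = 1.41, √3 = 1.73. At φ = 0.6, √0.6 = 0.77, so the printed error is too large.

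**Step 2: large-sample size of the Wald test.** This is 2 × [1 − Φ(1.96/√φ)]:
- φ = 0.6: 1.1%
- φ = 1.5: 11.0%
- φ = 2: 16.6%
- φ = 3: 25.8%

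**Step 3: simulated size at n = 30, mean 1, no true effect** (negative binomial counts, 10,000 runs).

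| φ | Wald, 15/15 factor | Wald, continuous factor | Pearson-scaled with t, 15/15 | Pearson-scaled with t, continuous | Sandwich (HC1) with t, continuous |
|---|---|---|---|---|---|
| 1.5 | 10.1% | 10.8% | 4.4% | 5.2% | 7.9% |
| 2 | 15.7% | 15.4% | 4.4% | 5.4% | 8.4% |
| 3 | 23.5% | 22.8% | 3.9% | 5.8% | 9.5% |

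A 20/10 split gives slightly lower Wald figures: about 9%, 14% and 22%. In simulation at φ = 0.6 (binomial counts, mean 0.8 to 1.2) the Wald test rejects about 1%.

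**Step 4: sensitivity.** Over n of 24 to 30, means of 0.5 to 2, and two-level or continuous factors, Wald size is about 6-11% at φ = 1.5 and 11-25% at φ = 3. Likelihood-ratio tests run at about 11-13% and 25-28%. At a mean of 0.5 with n = 30, the Pearson-scaled test is conservative for a 15/15 factor (2.7%, 2.2% and 1.4%) and near nominal for a continuous one (5.2%, 5.6% and 6.6%).

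**Step 5: could φ above 1 arise from the data collection?** Suppose T2 problems are exactly Poisson with mean λ and the visits are summed.
- If every problem is named again at T3 and none is new, the total is twice a Poisson count: variance 4λ, mean 2λ, φ = 2.
- If half persist and new problems with mean λ appear by T3, the mean is 2(λ/2) + λ/2 + λ = 2.5λ and the variance is 4(λ/2) + λ/2 + λ = 3.5λ, so φ = 1.4.

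These are illustrations. The plan does not say that it will sum the visits.

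**The case against.** **The plan already leaves room.** Section 17.2 allows another model form, so saying that it makes no allowance at all would go too far. But that option is listed as a remedy for separation, with no trigger and no named model. Overdispersion produces no fitting failure that would prompt its use.

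**Aim 2 is about effect sizes.** This is largely fair: no alpha is stated and low power is conceded. Yet 2.1 states directional hypotheses H2a to H2c, 17.5.1 speaks of hypothesis tests, and a strength of association needs an honest interval whether or not it is tested.

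**Overdispersion is not shown.** This is correct. No adverse-effect frequency is given, and counts of mostly none or one would make Poisson intervals too wide. That limits the claim but supports the remedy, because scaling corrects in both directions.

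**A stronger reading that fails.** A reader might infer that follow-up is unequal and that a time offset is needed. The visits are fixed for every user: "The second assessment (T2) will occur one month after the participant has been dispensed medical marijuana for the first time", and "T3 will occur 3 months after the participant has been dispensed medical marijuana for the first time". Dropout is the only planned source of unequal exposure, and 17.5.1 sends missing values to imputation. The prompt is also ambiguous between current and accumulated problems. If answers reflect current problems with equal means, and if 20% against 5% of two groups missed T3 (assumed rates), mean follow-up would be 0.80 × 3 + 0.20 × 1 = 2.6 against 0.95 × 3 + 0.05 × 1 = 2.9 months. An offset would then turn a true ratio of 1 into 2.9/2.6 = 1.12.

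**Conclusion.** The point holds for the count model only. The plan names plain Poisson regression for about 30 users without a dispersion check or a specific remedy. At an assumed 5% level and a mean near 1, Wald size would be about 10%, 15% and 23% at variance/mean 1.5, 2 and 3, with standard errors too small by a factor of 1.22 to 1.73. At 0.6 it would be about 1%. The dispersion, the mean and the alpha are all assumptions.

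It would be wrong to infer that every test of H2a to H2c is inflated. The same hypotheses are also examined by logistic regression on the 0/1 outcome, which overdispersion of the count does not affect. Because Aim 2 is secondary and framed around effect sizes, this is a worthwhile correction to the analysis plan and does not threaten the study's main conclusion.

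**What to change.** In 4.2 and 17.2, state that:
- each user contributes one count, the number of distinct problems reported at T2 or T3, with a problem named at both visits counted once;
- the Poisson model is fitted with standard errors scaled by Pearson chi-square divided by its degrees of freedom, with a t reference on n-2 df;
- results are reported as rate ratios with the resulting 95% intervals.

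Keep the existing exact or Firth options for separation, which scaling does not solve. Do not add a time offset. Do not offer sandwich errors as an equal alternative: at n = 30 and a mean of 1 they still reject about 8-9.5% for a continuous factor such as dose.

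The cost is two or three sentences and a standard option in Poisson software. Intervals widen when counts are overdispersed, and the test for a two-level factor becomes conservative if the mean is as low as 0.5 (about 1-3% at n = 30).

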### 17.3 Power Analysis

17.4 We compute the power to detect a medium effect size of 0.5 standard deviations across groups. Assuming a correlation of 0.2 across the repeated measures at three time points, the standard deviation of the average of three measures is 0.683 times the standard deviation of one measure. Therefore, with 31 per group we can detect a difference in this average of 0.5 times the standard deviation of one measure, using a two-sided test with 80% power. We calculated Cohen's d using [name] prior work that examined total driving errors and specific errors (Lane maintenance) in healthy controls ( $M= 24.08$   $SD=12.38$ ) and ( $M= 5.78$   $SD=4.26$ ) versus Parkinson patients ( $M=31.99$   $SD=22.01$ ) and ( $M=10.23$   $SD= 9.26$ ) which yielded a Cohen's d of .46-.65 (medium effect size); therefore we will be powered to detect this medium effect size.

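### Section 17.4 claims 80% power for a three-visit average that includes the pre-exposure visit; for a 0.5 SD effect after exposure, power at its own correlation is 33% to 72%

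*Combined protocol and SAP*

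**What the plan says.** Section 17.4 (Power Analysis) takes a medium effect of 0.5 SD between groups and a correlation of 0.2 among the three visits. It states that "the standard deviation of the average of three measures is 0.683 times the standard deviation of one measure" and that "with 31 per group we can detect a difference in this average of 0.5 times the standard deviation of one measure", two-sided, at 80% power. It then cites a healthy-versus-Parkinson comparison with Cohen's d of .46 to .65 and ends "therefore we will be powered to detect this medium effect size".

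The three visits are T1, T2 and T3 (sections 4.1.1 to 4.1.3). Sections 1.0, 6.1 and 6.2 place T1 before the first dispensation.

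For Aim 1, section 17.1 first plans between-group t-tests or Mann-Whitney tests, with no visit stated. It continues: "Repeated measures ANOVA will be used to examine within participants differences on measures at all 3 time points". The same sentence makes this analysis the one that decides whether exposure affects the three primary driving outcomes. It does not say whether time within users or group-by-time gives the answer.

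Section 6.1 sets 30 users and 30 controls. It gives the controls a specific job: "Control subjects will be used to ensure results are not attributed to a simple change in time". Users must report severe or chronic pain. For controls the text says "The control group will be matched by age, gender and race", and no pain criterion is stated.

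**The concern.** The quantity powered is not the effect the study asks about. Marijuana cannot affect a visit that precedes it, so including T1 dilutes any effect. The same average also absorbs any gap between users and controls that already existed at T1. Such a gap is plausible here, because pain is an entry criterion for users and is not a matching factor.

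Section 17.4 is the only power calculation in the documents, and it supports the primary aim. If it overstates the chance of detecting impairment, a non-significant Aim 1 result will look more reassuring about driving than it should. With the ANOVA term left open, the choice of contrast could also be made after the data are seen.

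**Working it through.** **Inputs.** From 17.4: effect 0.5 SD, correlation ρ = 0.2 for every pair of visits, two-sided test, 31 per group. From 6.1: 30 per group. Assumed: alpha 0.05 per test (none is stated; 0.05 reproduces the 31), no dropout, equal variances. Effect pattern: 0 at T1, because T1 is before exposure, and 0.5 SD at T2 and T3.

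**Step 1: the plan's own figure.** SD of the three-visit average = √((1 + 2×0.2)/3) = 0.683. Standardised difference = 0.5/0.683 = 0.732. The noncentral t gives 80.9% power at 31 per group and 79.6% at 30. The figure reproduces, and using 31 in place of 30 changes it by about one point.

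**Step 2: remove the effect from T1.** The average shifts by (0 + 0.5 + 0.5)/3 = 0.333 SD. Then 0.333/0.683 = 0.488, and power at 30 per group is 46%. To shift the average by 0.5 SD, the effect at T2 and T3 would have to be 0.5 × 3/2 = 0.75 SD at both visits.

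**Step 3: contrasts that could answer the exposure question** (30 per group, ρ = 0.2).
- Group-by-time F(2, 116): centred effects −1/3, 1/6, 1/6, sum of squares 0.1667; λ = (30/2) × 0.1667/0.8 = 3.125; power 33%.
- Change from T1 to the T2/T3 mean, users versus controls: SD = √((1+ρ)/2 + 1 − 2ρ) = √1.2 = 1.095; 0.5/1.095 = 0.456; power 41%.
- Users-only repeated measures ANOVA F(2, 58): λ = 30 × 0.1667/0.8 = 6.25; power 58%.
- Users-only paired change, 29 df: noncentrality 0.5 × √30/1.095 = 2.50; power 68%.
- T2/T3 mean, users versus controls, no T1: SD = √((1+ρ)/2) = 0.775; power 69%.
- T2/T3 mean adjusted for T1, 57 df: SD = √((1+ρ)/2 − ρ²) = √0.56 = 0.748; power 72%.

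A simulation of 20,000 runs agreed with each of these, and with the 46% in step 2, to within one percentage point.

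**Step 4: dependence on the correlation** (power for 0.5 SD at T2 and T3, 30 per group).

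| Contrast | ρ = 0.2 | ρ = 0.5 | ρ = 0.7 | ρ at which power reaches 80% |
|---|---|---|---|---|
| Three-visit average | 46% | 34% | 29% | not reached from 0.2 to 0.8 |
| Group-by-time | 33% | 49% | 72% | about 0.75 |
| Change from T1 | 41% | 59% | 81% | about 0.69 |
| T2/T3 mean alone | 69% | 59% | 54% | falls as ρ rises |
| T2/T3 mean adjusted for T1 | 72% | 77% | 89% | about 0.57 |
| Users-only ANOVA | 58% | 79% | 95% | about 0.51 |
| Users-only paired change | 68% | 86% | 98% | about 0.41 |

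The two users-only rows make no use of the controls, so any practice effect on the simulator would count as a marijuana effect.

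**Step 5: the plan's benchmark range.** For 0.46 to 0.65 SD at ρ = 0.2, power is 36% to 62% on change from T1 and 28% to 52% on group-by-time.

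**Step 6: a stable gap with no marijuana effect.** Suppose users and controls differ by the same amount at all three visits. For assumed gaps of 0.2, 0.3 and 0.5 SD at ρ = 0.2, the three-visit average is significant 20%, 39% and 80% of the time. The gap cancels in change from T1 and in group-by-time, so both stay at 5%.

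**The case against.** The strongest reply is that 17.4 is true as written. It says it powers a difference in the average, and 0.683 and 31 are correct. Aim 1 is worded as an association, 17.1 begins with between-group tests, and the benchmark is a cross-sectional group difference. A pattern of zero at T1 and 0.5 SD afterwards is not written in 17.4. All of that is fair, and the fault is not in the arithmetic. But the zero at T1 follows from the visit schedule. Reading 0.5 SD as a gap at all three visits counts a difference present before exposure as an effect of marijuana.

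Second, the role that 6.1 gives the controls points towards group-by-time, so the missing term can partly be inferred. That stands, but it points to the term with the lowest power, 33%. The upper part of the 33% to 72% range comes from contrasts the plan does not specify. For the two direct readings of the ANOVA in 17.1, group-by-time and users-only, the range is 33% to 58%.

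Third, the result depends on the correlation, and the documents give no evidence for any particular value. This also stands: at 0.7 the change contrast has 81% power. The value 0.2 is the plan's own, however, and the average it powers does worse as the correlation rises.

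Fourth, section 17.2 admits that power may be insufficient. That remark concerns Aim 2 and is not a calculation, so it does not qualify the Aim 1 claim.

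**Conclusion.** The concern holds. The 80% figure is correct for a 0.5 SD difference in the three-visit average, but it is not the chance of detecting a 0.5 SD effect that begins after T1. At the plan's correlation of 0.2 and 30 per group, that chance is 46% on the stated average. It is 33% to 72% on the contrasts that could address exposure, and none of those examined reaches 80%. Section 17.1 names the method but not the term that carries the conclusion. These figures rest on alpha 0.05, no dropout, equal correlations and the same effect at T2 and T3. A higher correlation would bring some contrasts above 80%, but not the three-visit average. This should be corrected, because the closing claim of 17.4 does not follow for the exposure question.

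**What to change.** In 17.1, name the term that answers Aim 1. A user-versus-control comparison of change from T1, either group-by-time or T1 against the T2/T3 mean, fits the purpose 6.1 gives the controls. A T1-adjusted comparison of the T2/T3 mean may be reported alongside. It needs a caveat: its adjustment slope equals the correlation, so at 0.2 it leaves 1 − 0.2 = 80% of any stable group gap in the estimate.

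In 17.4, use 30 per group, state alpha, and replace the 80% claim with detectable effects for the named term. Suggested wording: With 30 per group, two-sided alpha 0.05 and no dropout, change from T1 to the T2/T3 mean has 80% power for 0.81, 0.64 or 0.49 SD at correlation 0.2, 0.5 or 0.7 (group-by-time F test: 0.89, 0.70 or 0.54 SD). Limit the closing claim to effects those figures support.

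The cost is one sentence in 17.1, one rewritten paragraph in 17.4 and a less favourable stated power. No extra enrolment or procedure is proposed. For scale, 80% power for 0.5 SD on change from T1 would take 77, 49 or 30 per group at correlation 0.2, 0.5 or 0.7.

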### 17.5 Missing Data

17.5.1 We will handle missing data values with a 3-step process. First, the dropout rates will be compared across the groups with chi-square analyses to assess systematic differences due to condition. Second, demographic and dependent variables will be examined for their relationship to dropout. Those variables related to dropout status will be used to impute missing values for use in the analyses described (via SPSS Missing Items Analysis). Finally, comparison of the completers vs. imputation analyses will yield an additional estimate of the effect of dropouts on hypothesis tests.

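### Section 17.4's power holds for 31 evaluable participants per group at 0.5 SD, but the plan enrols 30 per group with no dropout allowance, and power at the lower cited effect of .46 is about 73%

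*Combined protocol and SAP*

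**What the plan says.** Section 17.4 (under 17.3 Power Analysis) sets the target: "We compute the power to detect a medium effect size of 0.5 standard deviations across groups". It takes the outcome as the mean of the three visits and fixes how strongly the visits are related: "Assuming a correlation of 0.2 across the repeated measures at three time points". From this it obtains a scale factor of 0.683 for the SD of that mean relative to a single visit. It then states the result: "Therefore, with 31 per group we can detect a difference in this average of 0.5 times the standard deviation of one measure". The test is two-sided and the power attached to this statement is 80%. No alpha is given.

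The same paragraph derives Cohen's d values of .46 (total driving errors) and .65 (lane maintenance errors) from a study comparing Parkinson patients with healthy controls. It labels them medium and ends: "therefore we will be powered to detect this medium effect size".

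Section 6.1 says "We will recruit N=60 participants total" and splits them into 30 users and 30 matched controls. Sections 1.0, 10.1 and 12.1 also give 60.

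Section 17.5 plans for losses: "First, the dropout rates will be compared across the groups with chi-square analyses". Imputation follows, and then a comparison with the completers analysis. Neither this section nor any other gives an expected dropout rate or adds participants to cover one.

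**The concern.** The power paragraph describes 62 evaluable participants; the rest of the protocol enrols 60. The figure of 31 is also the smallest group size that reaches 80%, so nothing is left to absorb losses, although each participant must complete three simulator visits and section 18.1.1 provides for stopping when motion sickness appears.

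The closing clause follows directly on a range whose lower end lies below the 0.5 SD used in the calculation. That lower end belongs to total driving errors, the broader of the two cited measures.

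What is at stake is how a null result for H1a to H1c would be read. A reader told that the study was powered for a medium effect would take a null finding as stronger evidence against such an effect than the enrolled design can supply.

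**Working it through.** The check takes section 17.4's contrast (between-group difference in the three-visit mean) and its correlation as given.

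**Inputs**
- Correlation 0.2, three visits, target 0.5 SD of one measure, two-sided test, 31 per group: section 17.4.
- Lower cited effect .46: section 17.4, put on the same scale as the 0.5.
- Enrolment of 30 per group: section 6.1.
- Two-sided alpha 0.05: assumed. It reproduces the plan's 31.
- Loss of 10% or 20%: assumed, as the plan gives no rate.

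**Step 1: SD factor.** √((1 + 2 × 0.2)/3) = √0.4667 = 0.683. This matches the plan.

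**Step 2: the plan's own figure.** The standardised effect is δ = 0.5/0.683 = 0.732. Power comes from the two-sample t-test, using the noncentral t distribution with 2n − 2 degrees of freedom and noncentrality δ√(n/2). With n = 31, the noncentrality is 0.732 × √15.5 = 2.88, the critical value is 2.00 and power is 80.9%. With n = 30, power is 79.6%. So 31 is the smallest n that reaches 80%, and section 17.4 is reproduced.

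**Step 3: the lower cited effect.** δ = 0.46/0.683 = 0.673. With n = 31, the noncentrality is 2.65 and power is 74.2%. With n = 30, it is 2.61 and power is 72.7%. Reaching 80% at 0.46 takes 36 per group.

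**Step 4: losses.** Here lost participants contribute nothing. A 10% loss leaves 30 × 0.9 = 27 per group; a 20% loss leaves 30 × 0.8 = 24.

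| Evaluable per group | Power at 0.50 SD | Power at 0.46 SD | Difference detectable at 80% power |
|---|---|---|---|
| 31 (section 17.4) | 80.9% | 74.2% | 0.494 SD |
| 30 (section 6.1, no loss) | 79.6% | 72.7% | 0.503 SD |
| 27 (10% loss, assumed) | 75.2% | 68.0% | 0.53 SD |
| 24 (20% loss, assumed) | 69.9% | 62.7% | 0.56 SD |

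At the upper cited effect of .65, power with 30 per group is 95.2%, so the shortfall is confined to the lower part of the range. The normal approximation gives slightly higher values (80.9% at 0.50 SD and 74.2% at 0.46 SD with 30 per group) and leads to the same conclusion.

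**The case against.** The strongest defence is that section 17.4 contains no calculation error. On its stated inputs, 31 per group at 0.5 SD gives 80%, and being one participant short in each group costs about one percentage point. All of that stands.

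A reader might go further and infer that the plan claims 80% power at every effect from .46 to .65. The text does not say so. It attaches 80% to 0.5 SD alone, and the cited values can be read as support for calling 0.5 medium. What remains is that the closing clause refers back to that range without qualification and gives no power for its lower end.

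A reader might also suspect that the d values themselves are miscalculated. The documents do not show this. Dividing each mean difference by the simple average of the two SDs gives 7.91/17.195 = 0.460 and 4.45/6.76 = 0.658, close to the stated .46 and .65. The source study's group sizes, which a pooled SD would need, are not given.

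On dropout, the loss rates above are assumptions, and treating lost participants as contributing nothing is the harsher reading. Section 17.5 plans imputation, and someone who misses only the last visit still supplies two. As an illustration, suppose 20% miss only T3 and the mean of the available visits is used, ignoring time trends. The average variance factor is 0.8 × 0.4667 + 0.2 × 0.6 = 0.493, and power at 0.5 SD with 30 per group is about 77% instead of 70%. This softens the loss but does not remove it, and it leaves the .46 result untouched.

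**Conclusion.** The point holds as an inconsistency and an unsupported conclusion, not as an arithmetic error. Three things stand:

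- Section 17.4 assumes 31 per group where section 6.1 enrols 30. The effect is minor: 80.9% falls to 79.6% at 0.50 SD.
- The sample size has no allowance for the dropout that section 17.5 expects. With 10% to 20% wholly lost, power at 0.50 SD would be about 75% to 70%.
- The closing clause does not hold at the lower cited effect, where power is about 73% before any loss and would be about 68% to 63% after it.

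The figures rest on a two-sided alpha of 0.05 and on the assumed loss range. They apply only to the contrast used in section 17.4, the three-visit mean, which includes the pre-exposure baseline. Section 17.1 plans t-tests or Mann-Whitney tests and repeated measures ANOVA, so these percentages should not be taken as the power of every analysis listed there.

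**What to change.** Rewrite the paragraph in section 17.4, keeping enrolment at 60:

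1. Use 30 per group, in agreement with sections 1.0, 6.1, 10.1 and 12.1.
2. State the alpha level, and an expected loss rate with its basis.
3. Give power at 0.50 and 0.46 SD both for 30 enrolled per group (79.6% and 72.7% if alpha is 0.05) and for the completers expected at that loss rate. The study team should supply the rate; 10% and 20% here are only illustrations.
4. Replace the closing clause with the difference detectable at 80% power: 0.503 SD with no loss, and about 0.53 or 0.56 SD if 10% or 20% were wholly lost.

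The cost is one paragraph of text and a less favourable power statement. No participants or visits are added. If the team would rather keep 31 evaluable per group, enrolment would have to rise to 35 per group at 10% loss (31/0.9 = 34.4) or 39 at 20% (31/0.8 = 38.75), but the correction does not depend on that.
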